## TRIAL OVERVIEW

**Title** Vitamin C, Hydrocortisone, and Vitamin B1 in Sepsis and Septic Shock – A Randomized, Double-Blind, Placebo-Controlled Trial (The ACTS Trial)

Clinical Trials Number	NCT03389555
Sources of monetary or material support	Open Philanthropy Project ( https://www.openphilanthropy.org/ )
Study Sites	12-sites in the United States
Condition studied	Sepsis and septic shock
Interventions	Vitamin C (1.5g every 6 hours x 4-days), hydrocortisone (50mg every 6 hours x 4-days), and Vitamin B1 (100mg every 6 hours x 4-days)
Comparator	Placebo
Inclusion criteria	

• Adult participant (age ≥ 18 years)

• Suspected (cultures drawn and antibiotic given) or confirmed (via culture results) infection

• Receiving vasopressor (norepinephrine, phenylephrine, epinephrine, dopamine, vasopressin, or angiotensin II)

Exclusion criteria	

• Member of a protected population (pregnant, prisoner)

• Known history of kidney stones within the past 1 year

• End stage renal disease (ESRD) requiring dialysis

• Known history of G6PD deficiency

• Known history of Hemochromatosis

• Comfort Measures Only status

• Anticipated death within 24-hours despite maximal therapy (as determined by the enrolling physician)

• Receiving supplemental vitamin B1 in a dose greater than that contained in a multivitamin (<2mg)

• Clinical indication for steroids (e.g. chronic use) as determined by the clinical team providing this drug

• Clinical indication for ascorbic acid supplementation in any form

• Clinical indication for vitamin B1 as determined by the clinical team providing this drug

• Known allergy to vitamin C, hydrocortisone, or vitamin B1

Study type	Interventional Allocation: Randomized (1:1) Intervention model: Parallel group Masking: Double-blind
Target sample size	200 Participants (100/arm)
Primary outcome	Change in the Sequential Organ Failure Assessment (SOFA) score between enrollment and 72-hours
Key secondary outcomes	Incidence of renal failure during index ICU stay 30-day mortality

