##### 5.1.2 Key Secondary Outcomes

Incidence of Acute Renal Failure – Renal failure will be defined as the development of Kidney Disease Improving Global Outcomes [KDIGO] Stage 3 acute kidney injury during the index ICU stay after study enrollment.

KDIGO Stage	Serum creatinine criteria	Urine output criteria
1	Increase in serum creatinine of more than or equal to 0.3 mg/dl ( $\geq$ 26.4 $\mu$ mol/l) or increase to more than or equal to 150% to 200% (1.5- to 2-fold) from baseline	Less than 0.5 ml/kg per hour for more than 6 hours
2	Increase in serum creatinine to more than 200% to 300% (> 2- to 3-fold) from baseline	Less than 0.5 ml/kg per hour for more than 12 hours
3	Increase in serum creatinine to more than 300% (> 3-fold) from baseline (or serum creatinine of more than or equal to 4.0 mg/dl [<math>\geq</math> 354 <math>\mu</math>mol/l]) with an acute increase of at least 0.5 mg/dl [44 <math>\mu</math>mol/l])	Less than 0.3 ml/kg per hour for 24 hours or anuria for 12 hours OR New renal replacement therapy (RRT)

**30-Day Mortality** – Mortality at 30-days. This will be assessed by review of the medical records if the participant remains in the hospital or if the participant expired while in the hospital. If the participant was discharged, 30-day mortality will be assessed by contacting the participant by phone or by searching the National Center for Health Statistics (NCHS) National Death Index (NDI) consistent with a recent multicenter phase III trial in sepsis. Phone calls will be made by the research team at each site.

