## 5.2 Rationale for Outcomes

**Change in SOFA score:** Organ failure is highly associated with mortality and improvement in organ function is a key goal for critical care physicians. In the study by Marik et al., participants who received the 3-drug regimen had substantial improvements in the trajectory of organ failure over the first 72-hours of their ICU stay. If the combination of vitamin C, hydrocortisone, and vitamin B1 can improve organ function in the first 72-hours following ICU admission, we believe that clinicians will likely quickly adopt this safe and inexpensive therapy. Importantly, this outcome can be measured early in the hospital stay and is therefore less likely to be affected by other potential elements of hospital care that can affect more distal outcomes (e.g., mortality).

**Kidney Injury:** Renal failure has been estimated to occur in 23% of participants with sepsis and over 50% of participants with septic shock. In studies of participants with septic shock, there is a step-wise increase in mortality with worsening acute kidney injury (AKI). In addition, many participants who experience renal injury during septic shock do not recover renal function prior to hospital discharge and may require long term dialysis. As both data from the study by Marik et. al. and a separate study of vitamin B1 in septic shock have shown substantial improvements in renal outcomes, kidney failure is a natural secondary outcome and one that could change practice independently from other factors – in other words, many clinicians would likely provide this therapy if they knew that kidney function could be protected, since this organ is vital to long-term health.

**Mortality:** Finally, we will measure 30-day mortality. We anticipate that the combination of vitamin C, hydrocortisone, and vitamin B1 will reduce mortality in this high-risk population.

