### 6.2.2 SOFA score and renal failure

The change in SOFA score will be calculated and compared between groups using the Wilcoxon Rank Sum test (if the change is not normally distributed) or by a t-test if the change is approximately normally distributed. Fisher's exact tests will be used to compare the incidence of renal failure during the index ICU stay.

If a participant expires prior to the 72-hour time point, SOFA scores will be imputed based on a pre-defined plan as follows. If a participant expires before 24-hours has elapsed, a 20% increase from baseline will be imputed. If a participant expires between 24-hours and 48-hours, a 15% increase from the 24-hour time point will be imputed. If a participant dies between 48-hours and 72-hours, a 20% increase from the 24-hour time point will be imputed. Sensitivity analyses will be performed using various other imputation techniques. Specifically, we will perform 1) a sensitivity analysis in which the worst possible SOFA score (score of 24) is imputed for those participants who expire, 2) a sensitivity analysis in which the last SOFA score for participants who expire will be carried forward, and 3) a sensitivity analysis in which only those patients who survive to 72-hours are included. These sensitivity analyses were chosen to model 'worst-possible' and 'best-possible' scenarios. For the secondary outcome of renal failure, participants who expire during their ICU stay will be assessed to have developed renal failure if they demonstrated any degree of unresolved KDIGO acute kidney injury prior to death. If there was no evidence of acute kidney injury prior to death or if kidney injury had fully resolved, these participants will be assessed as not having developed renal failure.

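### Renal failure is coded by one threshold in ICU deaths and another in survivors, 5.1.2 does not say so, and no renal sensitivity analysis would show how much mortality enters the comparison

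*Protocol*

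**What the plan says.** Protocol 5.1.2 defines the outcome as "development of Kidney Disease Improving Global Outcomes [KDIGO] Stage 3 acute kidney injury during the index ICU stay after study enrollment" and says nothing about participants who die. The trial overview names it "Incidence of renal failure during index ICU stay", and 6.2.2 says that Fisher's "exact tests will be used to compare the incidence of renal failure during the index ICU stay".

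Later in 6.2.2, participants who die in the ICU get a separate rule. They are "assessed to have developed renal failure if they demonstrated any degree of unresolved KDIGO acute kidney injury prior to death". If there was no injury, or if "kidney injury had fully resolved, these participants will be assessed as not having developed renal failure".

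The three sensitivity analyses in 6.2.2 come before the renal rule and are introduced as alternative SOFA imputations; the first is "a sensitivity analysis in which the worst possible SOFA score (score of 24) is imputed for those participants who expire". Neither document plans a sensitivity analysis for the renal outcome. SAP 5.1.2 and 6.2.2 carry the same definition and the same rule.

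**The concern.** Two identical kidney courses are coded by vital status:

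| Course after enrollment | Leaves the ICU alive | Dies in the ICU |
|---|---|---|
| Stage 1-2 only, unresolved | Non-event | Event |
| Stage 3, fully resolved | Event | Non-event |

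The first row lets deaths add renal events that do not meet 5.1.2. The second row removes cases that do meet it, which conflicts with an outcome described as incidence.

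Section 5.2 presents the renal outcome as "one that could change practice independently from other factors". If ICU mortality differs between arms, part of that difference can appear as a renal effect. Mortality is reported separately under 6.2.3, so a reader would see a mortality difference but could not tell how much of the renal result came from it.

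**Working it through.** **Inputs from the documents.** 100 per arm; renal failure 30% vs 55% with stated power 94% by Fisher's exact test; 30-day mortality 40% vs 20% (all Protocol 6.1); two-sided 0.05 (6.2.1).

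**Assumptions, not in the documents.** No treatment effect on stage 3, with the same rate *b* = 25, 30 or 35% in both arms. *u* = share of ICU decedents with only unresolved stage 1-2 injury, 10-50%. *r* = share of ICU decedents whose stage 3 had fully resolved, 0, 5 or 10%. *D* = ICU death rate in the arm. The low end of *u* is plausible, because 5.2 reports that mortality rises with injury stage.

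**Step 1, the plan's own figure.** Full enumeration of the two-sided Fisher test at 55% vs 30%, 100 per arm, gives 93.9%. The stated 94% reproduces.

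**Step 2, rate under the 6.2.2 rule.** Arm rate = *b* + (*u* − *r*) × *D*, so the difference produced by the rule alone is (*u* − *r*) × (*D*₁ − *D*₂). At deaths of 40% vs 20% and *r* = 0 it runs from 0.10 × 20 = 2 points to 0.50 × 20 = 10 points, against the planned renal effect of 55 − 30 = 25 points. Worked case: *b* = 30%, *u* = 50%, *r* = 0 gives 30 + 0.5 × 40 = 50% vs 30 + 0.5 × 20 = 40%.

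**Step 3, probability that Fisher's test is significant,** range over *b* and *u*:

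| ICU deaths | *r* = 0 | *r* = 5% | *r* = 10% |
|---|---|---|---|
| 40% vs 20% | 4.3-26.2% | 3.6-21.8% | 3.4-17.9% |
| 30% vs 15% | 3.9-16.1% | 3.5-13.6% | 3.4-11.4% |
| 20% vs 10% | 3.6-8.9% | 3.5-7.9% | 3.4-7.0% |
| 40% vs 32% | 3.6-7.3% | 3.5-6.6% | 3.4-6.1% |
| 40% vs 40% | 3.4-4.0% | 3.4-4.0% | 3.4-4.0% |

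The first row takes every 30-day death in 6.1 as an ICU death, so it is an upper end. Within it, at *r* = 0, *u* of 10-20% gives 4.3-7.0% and *u* of 30-50% gives about 11-26.2%. Without the rule, equal stage 3 rates give 3.4-3.5%.

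**Step 4, the alternatives.**
- *Stage 3 only.* Suppose a share *k* of ICU decedents would have reached stage 3 had they lived. The observed rate is *b* − *k* × *D*. At deaths of 40% vs 20%, *k* = 10, 20 and 30% give 4.3%, 7.1-8.0% and 12.5-16.4%, mostly favouring the arm with more deaths. At 20% vs 10%, *k* of 10-30% gives 3.6-5.8%.
- *Stage 3 or ICU death.* With *b* = 30% and half of decedents without stage 3, the rates are 30 + 0.5 × 40 = 50% vs 30 + 0.5 × 20 = 40%, significant in 26.1%.

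**The case against.** The rule is pre-specified in full in 6.2.2. The protocol also routinely defines outcomes in section 5 and handles deaths in section 6, as it does for SOFA and for ventilator- and shock-free days. The silence of 5.1.2 is therefore a missing cross-reference, not concealment. That stands.

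Counting ICU deaths with unresolved injury is one legitimate answer to death cutting off progression to stage 3, and neither alternative is shown to be less biased: step 4 gives up to 16.4% for one and 26.1% for the other. That also stands. It is the reason for leaving the main death rule in place and asking for results side by side.

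The 26.2% needs every 30-day death to occur in the ICU, mortality to be halved, half of decedents to have stage 1-2 injury only, and none to have resolved stage 3. If half of the 30-day deaths are ICU deaths (20% vs 10%, *b* = 30%, *r* = 0), the figure is 3.7-5.2% for *u* of 10-30% and 8.6% at *u* = 50%. The effect may be small, and the two clauses pull in opposite directions, so the documents do not fix the net direction. This limits the size of the problem. It does not answer two points: removing resolved stage 3 cases conflicts with the definition in 5.1.2, and no planned analysis would show how many renal events the death rule supplies.

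**Conclusion.** The concern holds. The documents code ICU deaths by a different threshold in both directions, 5.1.2 does not mention it, and no renal sensitivity analysis is planned. The resolved-stage-3 clause is wrong as written for an incidence outcome. The unresolved-injury clause is a defensible trade-off that needs labelling and a visible breakdown.

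The size is uncertain. With no stage 3 effect and ICU deaths of 40% vs 20%, the chance of a significant renal result is 4.3-26.2%, or 3.4-17.9% if 10% of decedents had fully resolved stage 3. It depends on the stage 3 rate, the injury mix among decedents and the ICU share of deaths, none of which the documents give. If ICU mortality and that mix are equal in the two arms, type I error is not inflated. The primary SOFA analysis and the mortality analysis are unaffected. This should be fixed because the outcome is a key secondary one and the repair is cheap.

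**What to change.** 1. In 6.2.2, count every participant who reaches KDIGO stage 3 after enrollment during the index ICU stay as an event, whether or not it resolved and whether or not the participant died.
2. In 5.1.2, cross-reference the remaining rule that an ICU death with unresolved stage 1-2 injury also counts.
3. In 6.2.2, pre-specify one renal sensitivity analysis: stage 3 only in all participants regardless of survival, shown beside stage 3 or ICU death, with both components by arm. The main Fisher analysis otherwise stays.

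Item 1 should not be made without item 3. It corrects stage 3 incidence but removes a partial offset: at 40% vs 20% deaths the upper end goes from 17.9% (*r* = 10%) to 26.2% (*r* = 0). The two results in item 3 must be read together, since stage 3 only can favour the arm with more early deaths and the composite is partly driven by mortality.

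The same edit could close two related gaps. The death rule in 6.2.2 does not repeat the after-enrollment condition of 5.1.2, and 6.1 does not say which coding its 55% and 30% follow.

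The cost is wording in 5.1.2 and 6.2.2 and one table. The present rule already needs injury stage, resolution and ICU death, so new data should not be needed, although the CRF variables are not shown (7.2).

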### 6.2.3 30-day mortality

Survival until 30 days will be analyzed using survival analysis. Participants lost to follow-up will be censored and the censoring will be assumed non-informative. Results will be presented with Kaplan-Meier curves and the groups compared using the log-rank test. Hazard ratios with 95% confidence intervals will be obtained using Cox's proportional hazards models. The proportional hazards assumption will be verified by visual inspection of the Kaplan-Meier curves and statistically by including a product term (i.e. "interaction") between the treatment group variable and the natural logarithm of time in the model. If the proportional hazards assumption is not met, only the Kaplan-Meier curves and the p-value from the log-rank test will be presented.

Adverse events and other binary outcomes will be presented and analyzed like renal failure.

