## 6. SAMPLE SIZE CALCULATION AND STATISTICAL ANALYSIS PLAN

### 6.1 Sample size calculation

The study has been powered to have at least 80% power for the primary outcome and all key secondary outcomes as follows:

**SOFA Score:** Based on preliminary data, we conservatively anticipate a decrease in SOFA score of 6 (standard deviation [SD]: 4) in the treatment group and 4 (SD: 2) in the placebo group. With these estimates, enrollment of **200 participants (100/arm)** at an alpha of 0.05 and using a t-test with unequal variance, the trial will provide > 99% power to detect a statistical significant difference between groups.

**Kidney Injury:** Based on preliminary data from our study of vitamin B1 in septic shock, we anticipate that 30% of participants in the treatment group and 55% in the placebo group will have renal failure which will result in a 94% power for this outcome. This calculation and following calculation were performed using the Fisher's exact test.

**Mortality:** Based on preliminary data, we anticipate that the control group will have a mortality of 40%. We estimate a treatment effect of 50% (risk ratio: 0.50) resulting in a mortality of 20% in the treatment group. With these estimates, 182 participants will lead to 80% power. To further increase

the trial's power and due to potential loss-to-follow-up, we will aim to enroll 200 participants. These estimates are conservative compared to the Marik et al. study which found a treatment effect corresponding to a risk ratio of 0.21 which persisted in adjusted analysis.

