### 706 *6.2.3 30-day mortality*

707 Survival until 30 days will be analyzed using survival analysis. Participants lost to follow-up will be  
708 censored and the censoring will be assumed non-informative. Results will be presented with  
709 Kaplan-Meier curves and the groups compared using the log-rank test. Hazard ratios with 95%  
710 confidence intervals will be obtained using Cox’s proportional hazards models. The proportional  
711 hazards assumption will be verified by visual inspection of the Kaplan-Meier curves and statistically  
712 by including a product term (i.e. “interaction”) between the treatment group variable and the natural  
713 logarithm of time in the model. If the proportional hazards assumption is not met, only the Kaplan-  
714 Meier curves and the p-value from the log-rank test will be presented.

715

716 Adverse events and other binary outcomes will be presented and analyzed like renal failure.

717

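### If the proportional-hazards check fails, 30-day mortality is left without a between-group estimate or confidence interval, although its sample size rests on 30-day risks

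*Protocol*

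**What the plan says.** Protocol section 6.2.3 assigns 30-day mortality to survival analysis: Kaplan-Meier curves, a log-rank test, and one effect measure, "Hazard ratios with 95% confidence intervals will be obtained using Cox's proportional hazards models". Proportional hazards is checked by looking at the curves and "statistically by including a product term (i.e. 'interaction') between the treatment group variable and the natural logarithm of time in the model". The section then states the consequence of a failed check: "If the proportional hazards assumption is not met, only the Kaplan-Meier curves and the p-value from the log-rank test will be presented". Both protocol texts reproduced in the SAP document carry the same rule in their section 6.2.3, leaving "Meier curves and the p-value from the log-rank test will be presented".

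Section 6.1 plans mortality on a different scale. Control mortality is taken as 40%, and "We estimate a treatment effect of 50% (risk ratio: 0.50) resulting in a mortality of 20% in the treatment group". It continues: "With these estimates, 182 participants will lead to 80% power". Of the test used, it says: "This calculation and following calculation were performed using the Fisher's exact test". The Sample Size Adjustment paragraph again expresses its mortality target as a 50% treatment effect.

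No section plans a risk difference, a risk ratio or any other fallback estimate for mortality.

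**The concern.** Mortality is one of two key secondary outcomes. Its only planned between-group estimate depends on a check made on the trial's own data, and a failed check removes the estimate without replacing it. The result would then be a p-value beside two curves, with no interval to show which sizes of benefit or harm remain plausible.

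Non-proportional hazards is a realistic possibility here. Study drug is given for at most 4 days (sections 2.3.1 and 4.4) while deaths are counted to day 30, so an effect could be concentrated early. The estimate is most likely to be withheld when the effect changes over time, which is when a reader most needs a plain 30-day contrast. Such a contrast exists whatever the shape of the hazards, and it is the scale on which mortality was powered.

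**Working it through.** **1. The plan's own figure.** Inputs from section 6.1: 40% vs 20%, two-sided 0.05, 80% power, 1:1.

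- Uncorrected n per arm = [1.96·√(2·0.3·0.7) + 0.8416·√(0.4·0.6 + 0.2·0.8)]² / 0.2² = (1.270 + 0.532)² / 0.04 ≈ 81.2, or 82 per arm (164 in total).
- With continuity correction: (81.2/4)·[1 + √(1 + 4/(81.2·0.2))]² ≈ 90.9, or 91 per arm. The total is **182**, as stated.
- Enumerating the two-sided Fisher test exactly gives 80.8% power at 182 and 84.4% at 200.

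The mortality calculation is therefore a comparison of 30-day proportions. By the same kind of formula, 80% power needs about 80 participants in total for SOFA and 136 for renal failure, so mortality is the most demanding of the three.

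**2. Whether another section fills the gap.**

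- The closing line of 6.2.3 analyzes adverse events and other binary outcomes in the same way as renal failure. Mortality has already been assigned to survival analysis, and renal failure itself has only a Fisher test with no named effect measure (6.2.2).
- Section 6.2.1 sets 95% coverage for intervals and cites CONSORT. It names no mortality estimate and does not lift the specific restriction in 6.2.3.

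**3. How often the restriction would apply.** The documents give no timing of deaths, so this part rests on assumptions. Setup: 100 per arm, censoring at day 30, a Cox model with group and group × ln(time), Wald test at 0.05, and 2,000 to 3,000 simulated trials per scenario. Control cumulative hazard to day 30 is −ln(0.6) = 0.511. The early-only effect is a hazard ratio of 0.3 or 0.5 for days 0–4 and 1 afterwards.

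| Share of control hazard in days 0–4 | Hazard ratio, days 0–4 | Product term p<0.05 |
|---|---|---|
| Proportional hazards, 40% vs 20% | 0.44 throughout | about 3–4% |
| 13% (constant hazard, 4/30) | 0.5 | about 9–10% |
| 13% | 0.3 | about 15–17% |
| 25% | 0.3 | about 30% |
| 47% | 0.5 | about 19% |
| 47% | 0.3 | about 44–48% |

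The bottom row is demanding. A 47% share is 0.47 × 0.511 = 0.240, which means control mortality of 1 − e^(−0.240) ≈ 21% by day 4. Treated 30-day mortality is then 1 − e^(−(0.511 − 0.7·0.240)) ≈ 29%. With a constant hazard and the same early hazard ratio of 0.3, it is about 37%.

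**4. What the missing estimate would look like.** Design rates, 100 per arm, complete follow-up (40 vs 20 deaths):

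- Risk difference: SE = √(0.4·0.6/100 + 0.2·0.8/100) = 0.0632. The 95% CI is 20.0 ± 12.4 points, or **7.6 to 32.4**.
- Risk ratio: SE of the log = √(0.6/40 + 0.8/20) = 0.2345. The 95% CI is 0.50·e^(±0.460), or **0.32 to 0.79**.
- Without censoring, the Greenwood standard error at day 30 equals the binomial one (0.049 and 0.040 for the two arms).
- No loss rate is given. With an assumed 10% loss (90 per arm), the half-width grows from 12.4 to 13.1 points and the ratio interval becomes 0.31 to 0.81.

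**The case against.** Withholding a single hazard ratio when hazards are not proportional is defensible, since one number would then average over a changing effect. That stands. The gap is that nothing replaces it.

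Three stronger readings are tempting, and the documents do not support them.

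- **That the estimate would be lost in nearly half of trials.** A figure near 45% needs both a strong early effect and about 47% of the control hazard in the first 4 days. The documents give neither, and section 3.3 excludes patients expected to die within 24 hours. It also treats the product term as the sole trigger, whereas 6.2.3 pairs it with visual inspection and does not say how the two combine or what threshold applies. Under the plan's own effect with proportional hazards, the restriction is rare.
- **That the result would show no size of effect, or could not be set against the planned risk ratio of 0.50.** Kaplan-Meier curves are presented in every case, so each arm's 30-day mortality can be compared with 40% and 20%. Under proportional hazards the design risks also convert directly: ln(0.8)/ln(0.6) ≈ 0.44. What is missing is the between-group contrast with its interval.
- **That the hazard ratio should give way even when proportional hazards holds.** That is a preference about the effect measure, not the correction of an error.

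Two smaller limits also stand. With censoring, a 30-day risk needs participants still at risk near day 30 and the non-informative censoring that the plan already assumes; phone and National Death Index follow-up makes this a minor obstacle. And the risk scale is the basis of the mortality calculation only: the primary outcome is change in SOFA, with its own power statement.

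**Conclusion.** The point holds as a gap in reporting. On a failed proportional-hazards check, the plan as worded gives no between-group estimate and no confidence interval for a key secondary outcome, although an estimate on the scale used to power that outcome would be available.

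The chance of this happening cannot be fixed from the documents. It is about 3–4% under proportional hazards and roughly 9–48% under assumed early-only effects (hazard ratio 0.3 to 0.5 for 4 days, then 1; 13% to 47% of the control cumulative hazard in days 0–4), taking p<0.05 on the product term as the trigger. The conclusion does not depend on where in that range the truth lies, because it follows from the wording of 6.2.3. The primary analysis, the validity of the log-rank test, the sample size and data collection are unaffected. The change is worth making because it costs almost nothing.

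**What to change.** In section 6.2.3 of the protocol and SAP, replace the sentence that restricts reporting with a rule of this kind: 30-day mortality in each arm, and the risk difference and risk ratio with 95% confidence intervals, are reported whatever the proportional-hazards check shows. Use Kaplan-Meier estimates with Greenwood standard errors if any follow-up is censored, and binomial estimates otherwise. Keep the log-rank test as the test, and keep the Cox hazard ratio where proportional hazards is acceptable. State how the visual check and the product term combine and at what threshold, so that the decision to show the hazard ratio is fixed in advance.

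The cost is a wording change and a line or two of output. No new data, no change of test and no change of sample size are needed.
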